2.8 STUDY ENDPOINTS

Principle Outcomes: The principle objectives for the pilot trial are to evaluate 1.) safety and efficacy and 2.) feasibility for a prehospital through in-hospital LTLR-WB resuscitation protocol that will lead to a large, multicenter clinical trial that can be performed under the requirements of *exception from informed consent for emergency research* with regulatory oversight by the Food and Drug Administration (FDA) and Title 21, Code of Federal Regulations, Section 50.24 (21 CFR 50.24).

Primary Outcome For Assessing Safety and Efficacy: The primary safety and efficacy outcome for the pilot trial will be all cause 28-day mortality. We will utilize data derived from our recently completed PAMPer trial, which utilized identical inclusion and exclusion criteria, for inhospital mortality estimates.

Primary Outcome For Assessing Feasibility and Trial Performance: The primary feasibility outcome for the pilot trial will be enrollment and accrual rate. Secondary performance and feasibility outcomes will include a) Eligibility rates; b) Adherence rates for the protocol; c) Injury and patient characteristics enrolled in the trial; d) Frequencies of proposed clinical outcomes; e) Air medical base population differences.

Secondary Clinical Outcomes Estimating Treatment Effectiveness and Safety: Over 28 days or up to discharge following randomization, we will compare: 1) Multiple Organ Failure (MOF): Organ dysfunction will be evaluated via the Denver Post-Injury Multiple Organ Failure Score and characterized as both a rate (%) and as MOF free days.^{84,85} 2) Mean Denver Post-injury MOF Score: This continuous variable will be a much more sensitive measure of organ dysfunction for the pilot trial. 3) Arrival Shock Severity: We will compare presenting base deficit,

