lactate and shock index (SI, heart rate/systolic blood pressure-bpm/mmHg) 4) Acute Respiratory Distress Syndrome (ARDS): We will compare pulmonary dysfunction using the Berlin definition for ARDS.⁸⁶ 5) Nosocomial Infection (NI): We will compare the incidence of pneumonia and blood stream infections. 6) Mortality: We will compare mortality rates at 3, 6 and 24 hours following arrival, all cause in-hospital and 28-day mortality. 7) Blood component transfusion and resuscitation requirements at 24 hours: We will compare overall blood component transfusion requirements and crystalloid/colloid resuscitation requirements across the two arms. 8) Acute Hemolytic Transfusion Reaction (AHTR): We will compare the incidence of AHTRs across study arms as defined by the CDC/National Healthcare Safety Network (NHSN) Hemovigilance Surveillance definition. (www.cdc.gov/nhsn) Length of hospital stay and intensive care unit stay. Length of stay and ICU resources will be descriptively compared. Patients will be followed for 28 days from admission for the 28-day mortality outcome utilizing chart review, patient contact or utilization of the social security death index for those who cannot be contacted.

Predefined Subgroup Analyses: Predefined subset analyses for the pilot trial will be performed looking at our primary outcomes (safety/efficacy and feasibility) in 1) Females > 50 years of age versus study cohort with females < 50 years excluded ; 2) Patients who ultimately did or did not require in-hospital blood transfusion; 3) Patients with and without significant traumatic brain injury (Head abbreviated injury score- AIS >2); 4) Patients enrolled from the scene of injury versus those enrolled from a referral hospital; 5) Patients that require operative intervention in the first 24 hours; 6) Those patients with a preinjury history of anticoagulation / antiplatelet therapy; 7) Patients who ultimately did or did not require massive transfusion (≥ 10 units blood in first 24 hrs) 8)Patients who did or did not receive prehospital PRBCs.

Clinical Outcome Definitions:

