Multiple Organ Failure (MOF): Organ dysfunction will be evaluated via the Denver Post-injury Multiple Organ Failure Score, a well-validated scoring system in injured patients and characterized as an incidence rate (%) and as MOF free days.^{84,87} Patients who are never admitted to the ICU or those with a length of ICU stay of less than 48 hrs will be considered to have a Denver score of 0. A summary of the Denver score may be calculated by summing the worst scores of each of the individual systems over the course of the ICU stay. A summary Denver score > 3 will be classified as MOF. Scores will be determined daily up until ICU discharge.⁸⁷ Mean Denver Post-injury MOF Score: As the primary endpoint for the pilot trial, the 3 highest (worst) daily Denver scores will be averaged and compared across the treatment arms. Patient not in the ICU will be given a score of 0. Acute Respiratory Distress Syndrome (ARDS): The Berlin definition for mild ARDS (PaO_2/FIO_2 , ≤ 300 mm Hg + timing, imaging and origin criteria) will be utilized as a threshold value to determine the incidence of ARDS and will be further stratified into Moderate (PaO_2/FIO_2 , ≤ 200) and Severe (PaO_2/FIO_2 , \leq 100).⁸⁶(Nosocomial Infection (NI): The CDC criteria for the diagnosis of hospital acquired pneumonia and blood stream infection will be utilized (www.cdc.gov/nhsn) Mortality: We will derive the time to a mortality event from the time of admission for 6 hour and 24 hour mortality rates over the initial 24 hours. All cause in-hospital and 28-day mortality will be similarly determined from the date of admission. 7) Blood component transfusion and resuscitation requirements at 24 hours: Blood component transfusion needs per unit (PRBC, FFP, PLT) will be recorded over the first 24 hours of admission with 6-hour incremental totals. For every unit of LTLR-WB that is transfused each will be designated as 1 unit of PRBC, 1u of FFP and a single pack of platelets. Similar recording of crystalloid volume and colloid volume of the initial 24 hours following admission will be undertaken. 8) Acute Hemolytic Transfusion Reactions: We will compare the incidence AHTRs (CDC NHSN Hemovigilance Surveillance definition) and will measure arrival serum haptoglobin levels. 9) Length of hospital and intensive care unit (ICU) stay: Length of stay will be determined from the date of admission for all enrolled patients.

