2.9 STATISTICAL ANALYSIS

The overarching goals for the pilot trial are to evaluate safety, efficacy and feasibility of a LTLR-WB prehospital through in-hospital protocol to plan for the successful execution of a large, multicenter clinical trial. All analyses will be performed based on the intent-to-treat principle for the prehospital randomization and analyses will include all enrolled patients grouped by randomization assignment. This pilot study will guide the calculation needed for the large, multicenter clinical trial and will provide estimation for intra-cluster correlation coefficient and sample size variation across clusters. We will report 95% confidence intervals for all measurements

Safety and Efficacy Analysis: 28-day mortality is the primary safety and efficacy outcome and will be compared across randomized groups. Utilizing intention to treat principles we will compare the LTLR-WB and Standard of Care arms using a pooled Z test for comparing two independent proportions. We will additionally perform survival analysis for all mortality outcomes including 3hr, 6hr, 24hr, and 28day time points across the two arms of the study testing the differences using log rank test.

Eligibility, Enrollment, and Subject Accrual Anlaysis: The feasibility of enrollment will be evaluated by determining 1) the number of patients that meet the eligibility criteria for the trial; 2) the proportion of eligible patients that can be randomized and 3) the proportion of eligible patients who are enrolled in the trial. These proportions will be estimated directly as the observed ratio of numbers of patients, and 95% confidence intervals will be calculated to understand the likely range of values for a larger study with a comparable research protocol. The reasons why patients are not enrolled including frequencies of individual exclusions and the proportion of patients declining participation or not able to be randomized will be described. Rate of subjects' accrual per month with 95% C.I. will be calculated.

Adherence and Minimization of Bias: Adherence rates for each treatment arm of the protocol will be ascertained as the proportion of enrolled patients who adhere to the intervention (LTLR-WB vs. standard care) as assigned. Estimated proportions and 95% confidence intervals will be created. The trial has been designed to negate intervention arm crossover and maximize follow-up completion.

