Estimates for Trial Secondary Clinical Outcomes: We will estimate the mean differences in the average Denver post-injury MOF score derived from the 3 highest daily scores between two treatment groups as the main clinical outcome for the pilot trial. We will also record and compare the overall proportion of patients who developed MOF based on Denver score > 3 and compare MOF free days. Similarly, the incidence of ARDS, NI, mortality (6hr, 24hr and 28 day) and hemolytic transfusion reactions will be recorded. We will perform survival analysis for all mortality outcomes. Blood component and resuscitation volumes over the initial 24 hours, length of ICU stay, days on a ventilator, and total hospital stay will be also be determined. Estimated proportions and means and 95% confidence intervals will be created for each outcome using the data from the entire pilot trial (i.e. combining the data from the two assigned treatment arms). Absolute and relative differences for continuous levels and event rates by assigned treatment will be estimated and 95% confidence intervals will be calculated to identify potential treatment differences for safety and for study planning purposes. Subgroup analyses will be exploratory and be based on baseline factors specified prior to the initiation of the trial.

The Following Outcomes Will Be Recorded:

- 1. The average Denver post-injury MOF score derived from the 3 highest daily scores. Differences between these averages will be estimated across the study two arms.
- Proportion of patients who developed MOF based on Denver score > 3 and compare MOF free days across the study two arms.
- 3. The incidence of ARDS, NI, mortality (6hr, 24hr and 28 day) and hemolytic transfusion reactions will be recorded and compared across the study two arms
- 4. Survival analysis in relation to all causes of death.
- 5. Blood component and resuscitation volumes over the initial 24 hours,
- 6. Length of ICU stay, days on a ventilator, and total hospital stay will be also be determined.

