Sample Size Justification for Pilot Trial: Assuming a baseline in-hospital mortality risk of 33% in the control arm as was demonstrated in the recently completed PAMPer trial with all cause in-hospital mortality as the primary outcome, enrolling **56 patients in each arm, 112 total patients** and using a 2 sided alpha of 0.05, the study will have a 80% power to detect a 22% (33% to 11%) or greater difference in in-hospital mortality. Based upon current PAMPer clinical outcome data and the additional benefit attributable to LTLR-WB when it is initiated in the prehospital setting, the current proposed mortality difference is clinically meaningful and of sufficient magnitude to influence clinical practice for a pilot trial. The above sample size will provide more than sufficient power for the originally planned feasibility outcomes as we have increased our sample size by 24%. The above power analysis was generated assuming 2 sequential tests using the O'Brien-Fleming spending function to determine test boundaries which are depicted in the following table and graph.

Details	Details when Spending = O'Brien-Fleming, N1 = 56, N2 =56, P1 = 0.1100, P2 = 0.3300							
		Lower	Upper	Nominal	Inc	Total	Inc	Total
Look	Time	Bndry	Bndry	Alpha	Alpha	Alpha	Power	Power
1	0.50	-2.96259	2.96259	0.003051	0.003051	0.003051	0.164669	0.164669
2	1.00	-1.96857	1.96857	0.049002	0.046949	0.050000	0.636252	0.800921
Drift 2.	81024							

Based upon the busy air medical service at the University of Pittsburgh, the bases to be utilized for the pilot trial, 61 patients who met all inclusion and exclusion criteria for the current proposed pilot trial, were admitted to Presbyterian Hospital, consented and were enrolled (www.pamperstudy.com) over a 12 month period 6/2015-5/2016. Based upon a planned enrollment period of 2.5 years, this sample size is feasible after accounting for consent rates and exclusions.

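### ICU stay, ventilator days and hospital stay are compared over all enrolled patients with no handling of death, so the raw contrast favours the arm with more deaths if those who die have shorter stays.

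*Combined protocol and SAP*

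**What the plan says.** Under the outcome definitions in section 2.8, item 9 covers hospital and ICU stay: "Length of stay will be determined from the date of admission for all enrolled patients". Section 2.9 sets the analysis population for every analysis: "analyses will include all enrolled patients grouped by randomization assignment". Ventilator days are not in item 9. They appear in section 2.9 ("length of ICU stay, days on a ventilator, and total hospital stay will be also be determined"), in the data list of section 6.5.1 and in Appendix 8 Table 4.

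The summary measures come from two statements in section 2.9. The first, "Estimated proportions and means and 95% confidence intervals will be created for each outcome", refers to the two arms combined. The second sets the contrast: "Absolute and relative differences for continuous levels and event rates by assigned treatment will be estimated", with 95% confidence intervals, for safety and for planning the later trial. Medians and interquartile ranges are planned as well. Appendix 8 Table 4 gives each of the three durations a row in days, with a column per arm and one for the 95% interval.

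The plan limits this comparison itself. Section 2.8 says "Length of stay and ICU resources will be descriptively compared", and Table 4 has no testing column, unlike Table 2.

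No section gives a rule for deaths in these three outcomes: no free-day form, worst rank, competing-risk analysis or split by vital status. A free-day form is planned for multiple organ failure only, and there too the scoring of deaths is not stated.

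**The concern.** A patient who dies within hours of arrival contributes close to zero ICU, ventilator and hospital days. In a raw comparison over all enrolled patients, that looks the same as a quick recovery. The trial expects such deaths: it compares mortality at 3, 6 and 24 hours and is designed around a large mortality difference.

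If whole blood keeps alive patients who would otherwise have died early, those patients go on to accumulate days, and the raw durations can move against the treatment for that reason alone. If whole blood caused early deaths, the durations could move in its favour. Section 2.9 puts these differences to use for safety and for planning the multicentre trial. Section 6.4.2 has the DSMB follow secondary outcomes by arm and has them checked at the interim analysis with 95% intervals across arms. A contrast with a misleading sign could therefore reach people who act on it.

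**Working it through.** **Inputs from the plan (section 2.9).** Control mortality comes from "Assuming a baseline in-hospital mortality risk of 33% in the control arm"; whole-blood mortality is 11%; there are 56 patients per arm. The plan's power figure, from which the two mortalities are taken, reproduces: the pooled drift is 0.22 / √(2 × 0.22 × 0.78 / 56) = 2.8102 (stated 2.81024), and the two-look power is 0.8010 (stated 0.800921). The plan states no figure for any duration.

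**Inputs assumed.** The documents give no stay data. Let S be the mean stay of survivors and D the mean stay of patients who die, equal in both arms, so that treatment has no effect on stay itself. I use S and D of 6 and 1, 8 and 2, and 10 and 2 ICU days.

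**Formula.** Arm mean = (1 − p) × S + p × D, where p is mortality. The higher-mortality arm is therefore shorter by (mortality gap) × (S − D).

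| S / D (days) | Mean at 33% mortality | Mean at 11% mortality | Difference |
|---|---|---|---|
| 6 / 1 | 0.67×6 + 0.33×1 = 4.35 | 0.89×6 + 0.11×1 = 5.45 | 1.10 |
| 8 / 2 | 0.67×8 + 0.33×2 = 6.02 | 0.89×8 + 0.11×2 = 7.34 | 1.32 |
| 10 / 2 | 0.67×10 + 0.33×2 = 7.36 | 0.89×10 + 0.11×2 = 9.12 | 1.76 |

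For longer stays, S from 10 to 20 and D from 1 to 4, the difference runs from 0.22 × (10 − 4) = 1.3 to 0.22 × (20 − 1) = 4.2 days.

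**Dependence on the gap.** With 8 and 2 days and a 5-point gap, the difference is 0.05 × 6 = 0.3 days. With no gap it is zero.

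**Offset by a real effect.** In the 8 and 2 day case, whole blood would have to shorten survivors' ICU stay by 1.32 / 0.89 = 1.5 days for the two raw means to be equal.

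**Medians.** If deaths hold the shortest stays, the all-patient median falls at the survivors' percentile (0.50 − p) / (1 − p). That is 0.17 / 0.67, the 25th percentile, at 33% mortality, and 0.39 / 0.89, the 44th percentile, at 11%. The median is pulled in the same direction as the mean.

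**Free days.** ICU-free days to day 28, death scored 0, with S = 8: 0.67 × 20 = 13.4 against 0.89 × 20 = 17.8. The arm with fewer deaths now comes out ahead by 4.4 days. Survivors' stay is equal in this example, so all of the 4.4 days comes from mortality.

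**The case against.** The strongest reply is that the plan already treats these rows modestly. The comparison is called descriptive, section 2.9's numbered list says only that the durations will be determined, and no test, decision rule or stopping boundary uses them. Bed-days per enrolled patient, with deaths counted as they occur, are also a proper measure of resource use, and section 2.8 speaks of ICU resources. Mortality at 6 hours, 24 hours and 28 days stands in the same Table 4. This limits the weight of the point. It does not remove it, because section 2.9 also plans by-arm differences with intervals for safety and planning, and a descriptive label does not change the sign of a difference.

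The size is open to challenge too, and here the reply largely stands. The stays are assumed, and 22 points is the difference the trial is powered for, not a forecast. With 56 per arm a 95% interval for a difference in means has a half-width of 1.96 × √(2/56) = 0.37 standard deviations. At an assumed standard deviation of 8 to 10 days that is about 3.0 to 3.7 days, wider than the 1.1 to 1.8 days above. Late deaths after long ICU stays would shrink the artefact further.

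A reader might infer that whole blood, if it works, is bound to appear to lengthen stay. The documents do not support this: it needs decedents to stay clearly less than survivors and no offsetting gain among survivors. A reader might also infer that the raw durations are wrong and should be removed. They are legitimate as resource use. Free days have their own weakness, since they carry the mortality difference themselves.

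**Conclusion.** The gap is real and of moderate weight. Followed as written, the plan yields by-arm contrasts in three secondary outcomes that lean towards the arm with more deaths whenever decedents stay less on average than survivors. That the deaths enter at their observed durations is an inference, drawn from the all-enrolled population and the absence of any other rule; the plan does not say it in words. Early deaths make the direction plausible, but no stay data in the documents confirm it. The 1.1 to 1.8 day figure rests on the full design gap, on the assumed stays and on equal stays in both arms by vital status. The planned medians do not cure the problem. The effect is confined to these duration rows and their use in safety review and planning.

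**What to change.** In section 2.8 item 9, section 2.9 and Appendix 8 Table 4:

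- Add ICU-free, ventilator-free and hospital-free days to day 28, with death by day 28 scored 0. Compare the arms by a rank-based method with a 95% confidence interval, for example the Mann–Whitney probability. State that these rows are the ones used for any between-arm reading of benefit or harm, including by the DSMB.
- Keep the three raw durations as descriptive resource-use rows. Label them as including deaths, show them by vital status as well, and note that they are not to be read as treatment benefit. The split by vital status conditions on an event after randomisation, so it too is description only.

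The cost is wording and three table rows. ICU days, ventilator days and length of stay are already collected (section 6.5.1), and 28-day vital status is already followed up (section 2.8). The downside is that free days mix death with duration, partly restate the mortality result, and must be read beside it.

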2.3 STUDY INTERVENTION

The study intervention will be the initiation of prehospital through in-hospital transfusion of LTLR-WB in patients meeting all inclusion and no exclusion criteria. Whole blood units will be obtained from a local FDA licensed blood center (LifeSource dba Central Blood Bank; Registration number: 2571073; License number: 1025).

Up to two units of LTLR-WB (O+) will be initiated in the prehospital phase of the study with an additional 6 units of LTLR-WB (O+) available during the in-hospital phase of the trial if indicated.

Study Intervention Rationale: To provide the earliest and most robust intervention with appropriate concern for blood banking resource utilization, a prehospital and in-hospital phase intervention will be utilized. As whole blood resuscitation is most pertinent to patients with acute hemorrhage, we have limited the in-hospital acute resuscitation phase time period and the additional 6 units of LTLR-WB to 4 hours post-admission. This acute phase resuscitation period definition is based upon unpublished data from the recently completed PAMPer study at our institution.⁴⁰ Over 79% of the blood products transfused in the first 24 hours occurred in the first 4 hours following admission.

Whole Blood Intervention: Blood from male only, group O+ donors will be collected using the FDA approved Terumo Imuflex® WB-SP blood bag system. With this collection system, whole

blood passes through a platelet sparing inline leukoreduction filter into a bag containing citrate phosphate dextrose solution. Male only whole blood donors will be used in order to mitigate the risk of transfusion related acute lung injury (TRALI; estimated incidence ≈1:12,000). Whole blood collected with this system can be kept as such for up to 21 days when stored between 1-6°C. Per blood bank protocol, the anti-A and anti-B antibody titers in each unit will be tested on a sample from every donor using an immediate spin saline tube method without incubation; only units where the titer of both anti-A and anti-B are <100 will be issued for the study and subsequent transfusion. All other required transmissible disease testing will also be performed on these LTLR-WB units before they are released, as per blood bank standard practice. The LTLR-WB units will have affixed on them the standardized Whole Blood product label thereby making them easily distinguishable from the other non-WB units in inventory.

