2.4 INTERVENTIONAL ARM

Prehospital Phase Interventional Arm: Two units of LTLR-WB (O+) will be stored at each helicopter base in temperature regulated blood bank approved refrigerators for up to 14 days, which is the period within which cold stored platelets are thought to retain maximal function. Two units of LTLR-WB will be transported on all air medical flights with prehospital staff in blood banking approved and verified coolers. The temperature of the blood will be monitored throughout transit and storage in accordance with standard blood banking and Stat MedEvac procedures. Following 14 days without use, LTLR-WB will be replaced with new LTLR-WB units and the old products will be returned to the blood bank for recycling into PRBCs.. During transport, storage and during all flights standard STAT MEDEVAC protocols for storing and carrying blood products at the base and on the helicopters will be followed. While at the bases the blood units are stored in a dedicated blood refrigerator and moved to cooler for transport only when the aircraft is launched. The blood is packaged in the coolers with a thermometer for temperature maintenance to assure that they are maintained at 2-5 degrees Celsius at all times. The Clinical Protocol that is currently followed and will be followed for all blood products in the study can be found in Appendix 1. Our FDA approved blood bank will follow all regulations required by the FDA for safe blood and blood component transfusion. On day 15, after ensuring the WB unit had remained in temperature compliance and is otherwise eligible for recycling according to 21 CFR 640.2(c), the WB unit will be recycled into a PRBC unit following the standard operating procedures at the Centralized Transfusion Service in Pittsburgh.

Patients who meet all inclusion and no exclusion criteria at the scene, at a referral hospital or during transport and are randomized to the interventional arm will receive up to 2 units of LTLR-WB (O+) en-route to a PPOWER participating trauma center based upon hemodynamic status using identical criteria as the Prehospital Standard of Care arm. If the intervention is completed during transport, standard operating procedures for the prehospital setting will be employed by the prehospital providers during the remaining flight. (Appendix 7)

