In-Hospital Phase Interventional Arm: Once enrolled in the interventional arm, prehospital providers will inform the trauma team of PPOWER enrollment and the randomization of the patient into the interventional arm (LTLR-WB administration arm). Upon arrival and on-going in-hospital LTLR-WB transfusion will be at the discretion of the trauma attending/team based upon the hemodynamic status of the patient, injury severity, need for therapeutic intervention, control of hemorrhage and on-going coagulopathy.

Patients enrolled in the interventional arm will only receive LTLR-WB if blood products are required during the acute resuscitation phase over the first 4 hours following admission (up to 6 units of LTLR-WB). The acute resuscitation phase generally includes the first 4 hours from the time of admission. Six units of LTLR-WB will be available for urgent release in the emergency department and will be taken to the operating room as needed. In those patients with ongoing

hemorrhage who require blood products beyond the 8 units of LTLR-WB total (2 prehospital, 6 inhospital), a balanced component transfusion strategy will be employed identical to the standard of care arm of the study and usual care at the University of Pittsburgh.

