Mechanistic Outcomes: The principle factors that may be responsible for beneficial clinical outcome effects associated with or attributable to LTLR-WB resuscitation when initiated early in the prehospital phase of injury are an important and essential objective of the proposed pilot trial. We will compare across treatment arms: 1) Coagulopathy: Coagulopathy will be assessed via PT/PTT/INR and rapid Thromboelastography (r-TEG) measurements. 2) Platelet Function: We will assess platelet activation, aggregation, and adhesion via flow cytometry analysis, whole blood aggregometry measurements and flow chamber analysis under shear stress conditions, respectively in a subset of patients.^{88,89} 3) Glycocalyx integrity: We will assess glycocalyx integrity by measuring serum concentrations of Syndecan-1 and Hyaluronan by ELISA at inhospital time points. 3) Donor Exposure, Age and Volume of Transfusion Products: During the prehospital and in-hospital acute resuscitation phase of the study the number donors from all transfused products blood products, the age of all LTLR-WB and PRBCs from the standard of care arm and overall transfusion volumes will be recorded and compared.

Blood Sampling and In-Hospital Measurements: In-hospital phase blood sampling will occur upon arrival (+ 4 hrs) and at 12 hours (+/- 12hrs) and 24 hours (+/- 12hrs) from time of arrival. Timing of samples will need to be flexible based upon patient availability and logistic factors. This early in-hospital sampling will allow adequate assessment of the benefits of early LTLR-WB resuscitation and appropriate characterization of the proposed clinical and mechanistic outcomes. TEG analysis at arrival, 12hr and 24hr time points will be performed on a TEG[®] 5000 Thromboelastograph[®] Hemostasis Analyzer.

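### Storage age is specified for PRBCs in the standard of care arm only, so the planned age comparison leaves out part of the LTLR-WB arm's red-cell exposure and compares products, not randomised patients

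*Combined protocol and SAP*

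**What the plan says.** Section 2.8 introduces the mechanistic outcomes as comparisons between the treatment arms. The item on donor exposure, product age and volume has two parts.

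- **Donors.** The count is set out as "During the prehospital and in-hospital acute resuscitation phase of the study the number donors from all transfused products blood products". It has no arm restriction.
- **Age.** The rule is that "the age of all LTLR-WB and PRBCs from the standard of care arm and overall transfusion volumes will be recorded and compared". PRBC age is tied to one arm.

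Section 2.4 states that when an LTLR-WB patient needs more than eight whole-blood units (two prehospital, six in hospital), "a balanced component transfusion strategy will be employed identical to the standard of care arm". That strategy contains PRBCs. On the window, the same section says "The acute resuscitation phase generally includes the first 4 hours from the time of admission".

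Section 2.9 requires all analyses to follow intent-to-treat, with every enrolled patient grouped by assignment.

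**The concern.** Specific Aim III asks what drives any benefit of LTLR-WB, and section 1.3 lists a reduced storage lesion among the candidate explanations. Testing that explanation requires knowing how old the red cells were that each randomised patient received.

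Under the age rule, an LTLR-WB patient who exhausts the whole-blood allotment and then receives PRBCs is described by the whole-blood units alone. A control patient is described by all of his or her PRBCs. The omission falls in one arm only, and among that arm's most heavily transfused patients. The result would answer whether LTLR-WB units are younger than PRBC units, which is a fact about inventory. It would not answer whether assignment to LTLR-WB lowered the storage age of the red cells patients received. A difference of the first kind could be carried into the design of the multicenter trial as if it were the second.

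**Working it through.** The plan gives no expected value, variance or power for storage age or donor exposure, so there is no figure to reproduce. The check has two parts: the effect of the age rule, and whether the donor count shares the defect.

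**Inputs from the documents**

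| Input | Value | Source |
|---|---|---|
| Ages recorded | All LTLR-WB; PRBCs in control arm | 2.8 |
| PRBCs possible in LTLR-WB arm | Yes, after 8 whole-blood units | 2.4 |
| Whole-blood storage at bases | Up to 14 days | 2.4 |
| Whole-blood storage limit | 21 days | 2.3 |
| PRBC age or shelf life | Not given; Appendix 1 has only a return rule relative to expiry | – |
| Share of 24-hour products given by 4 hours | Over 79% | 2.3 |

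**Storage age.** Let w be the mean age of LTLR-WB and p the mean age of PRBCs, assumed the same in both arms. Let D = p − w, and let s be the PRBC share of red-cell-containing units in the LTLR-WB arm.

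- Recorded difference (control minus LTLR-WB): p − w = D.
- Difference with all units counted: p − [(1 − s)w + s·p] = (1 − s)D.
- Overstatement: D − (1 − s)D = s·D.

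The documents give neither D nor s, so both are assumed and shown over a range. The body of the table gives the all-unit difference in days.

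| Assumed ages (w, p) | Recorded | s = 5% | s = 10% | s = 20% | s = 40% |
|---|---|---|---|---|---|
| 10, 10 | 0 | 0 | 0 | 0 | 0 |
| 10, 20 | 10 | 9.5 | 9.0 | 8.0 | 6.0 |
| 10, 30 | 20 | 19.0 | 18.0 | 16.0 | 12.0 |
| 14, 10 | −4 | −3.8 | −3.6 | −3.2 | −2.4 |

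In the last row PRBCs are the younger product, and the omission makes the LTLR-WB arm look worse than it is.

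For one LTLR-WB patient who receives k red-cell-containing units, eight of them whole blood, the PRBC share is (k − 8)/k: 0% at 8 units, 20% at 10, 33% at 12 and 50% at 16. With w = 10 and p = 20, the recorded mean age is 10 days in every case. The all-unit mean is (8 × 10 + 2 × 20)/10 = 12 days at 10 units and (8 × 10 + 8 × 20)/16 = 15 days at 16.

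**Donor count.** Take 10 red-cell equivalents over 24 hours, 79% of them in the acute phase, with one donor per whole-blood unit and three per 1:1:1 set (the donor numbers are assumptions).

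- Acute phase: control 7.9 × 3 = 23.7; LTLR-WB 7.9 × 1 = 7.9. Difference 15.8, ratio 0.33.
- 24 hours, equal late component use: control 10 × 3 = 30; LTLR-WB 7.9 + 2.1 × 3 = 14.2. Difference 15.8, ratio 0.47.
- 24 hours, late use halved in the LTLR-WB arm: 7.9 + 3.15 = 11.05. Difference 18.95.
- 24 hours, late use 1.5 times as high in that arm: 7.9 + 9.45 = 17.35. Difference 12.65.

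The acute window changes the ratio. It leaves the absolute difference unchanged when late use is equal, and otherwise the 24-hour difference may be larger or smaller.

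**The case against.** The strongest reply is that the gap is narrow. Section 2.4 restricts the LTLR-WB arm to whole blood in the acute phase until the allotment is used, so within that window essentially only patients above eight units are affected. The item is one mechanistic measure in a pilot, has no row in the Appendix 8 tables and carries no power claim. Section 2.9 already imposes analysis by assignment. The missing ages may also be recoverable: section 6.4.6 requires donation numbers in the record for prehospital transfusions, and the look-back procedure in Appendix 6 describes tracing units to recipients. All of this limits the size of the problem. It does not make the written rule consistent with section 2.9, and records that could be retrieved are not the same as a plan to retrieve them.

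A reader might go further and infer that the age and donor results both favour whole blood by construction. The documents do not support that.

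- **Age.** No PRBC age is stated, and whole blood may itself be up to 14 days old at the bases and 21 days overall. The direction depends on PRBCs being older, which is plausible but assumed.
- **Donors.** Components given to LTLR-WB patients in the acute phase are counted, and the window is the same in both arms. Section 2.3 justifies that window by the data: "Over 79% of the blood products transfused in the first 24 hours occurred in the first 4 hours following admission". Measuring an exposure over the period in which the intervention is delivered is a reasoned choice. Fewer donors per whole-blood unit is a property of the product, not a counting error.

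Nor should the 36% large-volume transfusion figure in section 2.2 be read as the share of patients affected. The volume is not defined there and cannot be equated with more than eight units in about four hours.

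**Conclusion.** The concern stands for storage age. Section 2.8 specifies PRBC age in one arm only, although section 2.4 provides for PRBCs in the other, so the comparison omits exposure on one side and is not a comparison of randomised arms. That inconsistency with section 2.9 does not depend on the direction of any bias.

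The numerical error is s × D. For an assumed D of 10 days it is 0.5 day at s = 5%, 2 days at 20% and 4 days at 40%. It is zero if the products are of equal age and reverses sign if PRBCs are younger. The calculation assumes that PRBCs have the same mean age in both arms and weights by unit. The true s will depend on how many patients exceed eight units, which the documents do not say.

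The donor count is not biased by its definition. The consequence is confined to a mechanistic outcome under Specific Aim III; 28-day mortality and the secondary clinical outcomes are untouched.

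**What to change.** Reword the item in section 2.8 so that storage age, counted from collection, is recorded for every red-cell-containing unit, LTLR-WB or PRBC, in both arms over the stated window. Compare per-patient mean and maximum red-cell age by assigned arm. These summaries exist only for patients who received red cells, so also report the number in each arm who received none. Age by product can stay as a descriptive line.

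A donor count through 24 hours, matching the window in which section 2.8 already records component units, is an optional extra row. If it is added, show absolute and relative differences together and keep the acute-phase count.

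The cost is a wording change, case report form fields for the extra units, modest data entry and possibly a smaller apparent contrast in storage age. Transfusion practice and the primary analysis do not change.
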